Study Design	
This is a prospective multi-center, double-masked, randomized, placebo-controlled clinical trial. Subjects will be centrally randomly assigned in a 1:1 ratio to receive one of the following treatments in the affected eyelid:
 
SUN-131 1.5% TDS (n = 130) Placebo TDS (n = 130)
 
The randomization will be stratified by age group (<12 years, ≥12 years). All study drug will be worn for a minimum of 16 hours and a maximum of 24 hours each day for 14 days.
 
The following items will be assessed at screening/baseline and at 30 minutes to 1 hour after patch removal on Days 8 ± 1 and 15 ± 1.
 
 • Presence of a chalazion by examination (clinical assessment) • [REDACTED] • Erythema of the chalazion site itself as measured by a 5-point scale (0 = no sign of erythema, 1 = slight erythema, 2 = mild erythema, 3 = moderate erythema, 4 = severe erythema) • Pain in study eyelid and eye of the study eyelid related to chalazion as measured by Visual Analog Scale (VAS) of 100 mm 
Patient Reported Outcome (PRO) will be assessed by a self-evaluation diary of chalazion (present or absent), completed daily by the subjects from Day 1 through Day 15 ± 1.

Sample Size	Approximately 260 subjects will be randomized.
Study Population	Male or female subjects aged ≥ 6 years with a chalazion
Inclusion Criteria	
Subjects eligible to participate in the study must meet all of the following criteria:
 
 1. Subjects aged ≥ 6 years of either sex and of any race. 2. Subjects with a diagnosis of a single chalazion with visible granuloma in the study eyelid. Study eyelid may be either an upper or lower eyelid. 3. Subjects with a chalazion with the granuloma area (height x width) ≤ 36 mm² when measured by a caliper. 4. Subjects with chalazion erythema score of ≥ 1 (as graded on a 5-point scale: 0 = no erythema, 1 = slight erythema, 2 = mild erythema, 3 = moderate erythema, 4 = severe erythema). 5. Chalazion intended for study treatment present for no more than 21 days based on patient history on Day 1. 6. Normal eyelid function without active signs of eye/eyelid infection in either eye.

[figure not shown]

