4.4 Method of Randomization and Treatment Assignment

Each subject who is entered into the study will be assigned a screening number. The screening number will consist of the 2-digit site number (##) and a 3-digit sequential number (XXX). The subject screening number (##-XXX) becomes the subject identifier.

For subjects who meet the criteria for randomization, a treatment group randomization code will be assigned to that subject number via an Interactive Web Response System (IWRS). Subjects will then be centrally randomized in a 1:1 ratio to either SUN-131 1.5% TDS or placebo TDS. The randomization will be stratified by age group (<12 years, ≥12 years).

Re-screening of the same subject that has previously screen failed is allowed only once. Re-entry of the same subject that was previously randomized is allowed only once. A new subject number will be issued when the same subject is re-screened or re-enrolled for the study.

The study drug kit will be coded with a three-digit (YYY) kit number. After randomization on Day 1, the IWRS will assign a study drug kit to a subject. On Day 1, the subject will receive a 1-week supply of study drug including backup study drug. On Day 8 ± 1, the subject will visit the site, return all used and unused study drug, and be provided with another 1-week supply of study drug including backup study drug. On Day 15 ± 1, the subject will visit the site and return used and unused study drug.

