5.10 Appropriateness of Measurements

The ocular safety measurements used in the study (AEs, VA, slit-lamp biomicroscopy, IOP measurement) are generally recognized as reliable, accurate, and relevant in assessing the safety of topical ophthalmic pharmaceutical drugs.

This is the first study to evaluate a transdermal delivery methodology for ophthalmic medication; it is thus considered appropriate to capture the subject’s impressions of ocular and dermal comfort during and after wearing the study drug. For both assessments, the subjects will use a 100 mm VAS, where 0 mm = very comfortable and 100 mm = very uncomfortable, to rate the comfort.

The Draize scale that will be used for scoring dermal response (see Table 2) caused by the study drug, as well as the scale that will be used to evaluate patch adhesion (see Section 5.4), have been widely used by all regulatory authorities for evaluation of skin irritation (4).

The primary endpoints are clinical evaluation of the eyelid and determination of the presence or absence of a chalazion. While slight scarring or distortion of the skin may remain due to the granuloma, the assessment of healing of the chalazion will be based on clinical judgment. Subjects who exhibit a complete resolution of the chalazion based on clinical examination at any time in the study will be considered a CR.

The secondary outcome measures include time to CR of the chalazion as documented by the subject in the patient diary. The size of the study chalazion will also be evaluated and its rationale given that complete resolution may not occur; however, the size of the chalazion may be significantly reduced with treatment. The erythema of the chalazion site itself will also be assessed using a 5-point scale common in ophthalmology for evaluating the redness of the chalazion. In some cases, the chalazion can cause pain either in the eyelid or the eye itself. As such, a pain VAS will be used to ask the subject to assess either the pain in the eyelid caused by the chalazion or the pain in the eye itself that may occur due to pressure on the eye from the chalazion.

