7 STATISTICAL METHODS AND DETERMINATION OF SAMPLE SIZE

7.1 Statistical and Analytical Plans

All data collected on CRFs will be presented in data listings. The primary and secondary endpoints for this trial will be evaluated using the Intent-to-Treat (ITT) population with the Modified Intent-to-Treat (mITT) performed as a sensitivity analysis. The safety analyses will be carried out using the safety population. Comfort scores (ocular, skin, and the average of both), patch adhesion, and residual drug content will be analyzed using the ITT population (and mITT and Per-Protocol [PP] populations if there are subjects with protocol deviations or incomplete data). In general, the grade for each measure in each eye will be used for analysis of treatment effects unless otherwise specified. All analyses will be conducted in a validated instance of SAS 9.1 or higher.

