7.1.5 Analysis of Efficacy

7.1.5.1 Primary Efficacy Analysis

The primary analysis will compare the proportions of subjects in the 2 groups who experience CR of the study chalazion on or before Day 15 \pm 1. CR is defined as the absence of any significant clinical signs of a chalazion with possible scarring or skin defects resulting from healing of the chalazion allowed. The primary analysis will be conducted using Pearson's chi-square test (two-sided) at the $\alpha = 0.05$ level of significance.

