7.1.5.2 Key Secondary Analyses

7.1.5.3 Other Efficacy Analyses

All quantitative secondary endpoints will be analyzed using the two-sample t-test (parametric) and the Wilcoxon-Mann-Whitney test (nonparametric). Secondary endpoints that are defined as time-to-event variables will be summarized using the Kaplan-Meier method; the log-rank test will be used to compare the distributions in the 2 groups. The primary and secondary endpoints will also be analyzed in the PP population. All secondary analyses will be conducted using two-sided tests at the $\alpha = 0.05$ level of significance.

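### Randomisation is stratified by age group, but the primary chi-square test ignores the stratum: the test stays valid, some power is lost if complete response differs by age, and a stratified test is a free, minor improvement.

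*Combined protocol and SAP*

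**What the plan says.** Section 4.4 (Method of Randomization and Treatment Assignment) states: "The randomization will be stratified by age group (<12 years, ≥12 years"). The Synopsis and sections 3.1 and 3.4.1 say the same. Age group is the only stratification factor named.

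Section 7.1.5.1 compares the proportions with CR on or before Day 15 ± 1: "The primary analysis will be conducted using Pearson's chi-square test (two-sided"), at the 0.05 "level of significance". It mentions no stratum.

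The other visible analyses of the primary endpoint change the population, not the method. Section 7.1 has the "Modified Intent-to-Treat (mITT) performed as a sensitivity analysis", and section 7.1.5.3 adds: "The primary and secondary endpoints will also be analyzed in the PP population". The t-test, Wilcoxon-Mann-Whitney test and log-rank test in 7.1.5.3 are also described without a stratum.

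The text of 7.1.5.2 (key secondary analyses) and 7.1.7 (sample size) is not shown in the public copy, so nothing is said here about what those sections contain.

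**The concern.** Stratifying the randomisation balances the arms within each age group. If age predicts CR, that balance makes the difference between arms less variable than under simple randomisation. Pearson's chi-square does not credit this: its variance comes from the pooled CR proportion, which includes the spread between age groups. The standard error is then too large, the actual type I error falls below 5%, and power is lost. What is at stake is a few points of power in a single-primary-endpoint Phase 3 trial, and an analysis that does not follow its own randomisation. The correctness of a positive result is not in question on this ground.

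**Working it through.** **Plan's own figure.** The plan gives 130 per arm, 1:1, two-sided alpha 0.05. That sample size cannot be reproduced, because the text of 7.1.7 is not shown.

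**Inputs.** From the documents: 130 per arm, alpha 0.05, two strata. Assumed: 20% or 30% aged under 12 (26 or 39 per arm), exact balance within strata, placebo CR by age as listed below, and an odds ratio of 2.1 in both strata. Active CR is p_A = 2.1p / (1 − p + 2.1p). For p = 0.35 this is 0.735/1.385 = 0.531, and the chi-square then has 84.5% power, a plausible design point.

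**Tests**, both without continuity correction, critical value 3.841. In stratum k, a_k is the number of active responders, m_k all responders, n_Ak and n_Pk the arm sizes, and N_k = n_Ak + n_Pk. Without the subscript k, these are totals over both strata (a, m, n_A, n_P, N).
- Pearson: X² = N[a(n_P − b) − b(n_A − a)]² / [n_A n_P m(N − m)], where b is the number of placebo responders.
- CMH: [Σ(a_k − n_Ak m_k/N_k)]² / Σ[n_Ak n_Pk m_k(N_k − m_k) / (N_k²(N_k − 1))].

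**Results**, by exact enumeration of all binomial outcomes, so without simulation error. Placebo CR is under 12 / 12 and over. Type I error uses an odds ratio of 1.

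| Placebo CR (%) | Share <12 | Power, chi-square | Power, CMH | Loss (points) | Type I, chi-square | Type I, CMH |
|---|---|---|---|---|---|---|
| 35/35 | 20% | 84.5% | 84.5% | 0.0 | 5.0% | 4.9% |
| 40/30 | 20% | 82.8% | 82.8% | 0.02 | 5.0% | 5.0% |
| 50/30 | 20% | 82.3% | 82.5% | 0.15 | 4.8% | 5.0% |
| 45/25 | 20% | 79.6% | 80.5% | 0.86 | 4.6% | 5.0% |
| 40/20 | 20% | 76.3% | 77.1% | 0.85 | 4.6% | 5.0% |
| 30/10 | 20% | 58.9% | 61.4% | 2.5 | 4.3% | 5.0% |
| 30/10 | 30% | 61.9% | 64.8% | 2.9 | 4.2% | 5.0% |
| 60/25 | 20% | 76.9% | 79.6% | 2.6 | 4.1% | 5.0% |
| 70/20 | 20% | 67.1% | 74.0% | 7.0 | 3.0% | 5.0% |

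**Hand check of the 70/20 type I error.** Pooled CR is 0.2 × 0.7 + 0.8 × 0.2 = 0.30, so the chi-square uses 0.30 × 0.70 = 0.210. The within-stratum variance is 0.2 × 0.21 + 0.8 × 0.16 = 0.170. The test statistic therefore has standard deviation √(0.170/0.210) = 0.90, and the two-sided error is 2[1 − Φ(1.96/0.90)], about 2.9%. The exact value is 3.0%.

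**Other assumptions.** A separate simulation set the odds ratio so that the chi-square had about 80% power, with 5-50% aged under 12 and overall placebo CR of 20-40%. The gain from CMH was −0.1 to 0.6 point for age gaps of 0-10 points, 0 to 2.3 at 20 points, 0 to 5.2 at 30, and 0 to 6.4 at 40. Chi-square type I error lay between 2.75% and 5.1%.

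**Cost if age does not matter.** With exact balance and placebo CR of 20%, 35% or 50% in both strata, CMH gives up at most 0.02 point. With 27 and 25 subjects under 12 in the two arms and placebo CR of 35%, it gives up 0.05 point.

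**Limit.** The table assumes exact balance. At 50/30 with 27 versus 25 subjects under 12, the difference is −0.3 point if the active arm has more of them and +1.6 points if the placebo arm does.

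**The case against.** The strongest reply is that this is a preference between two valid tests. Nothing visible promises a stratified analysis, so 4.4 and 7.1.5.1 do not contradict each other. Nothing visible suggests that CR depends on age: the Phase 2 trial in section 1.2 enrolled adults and no CR rate is shown for it. Every input that drives the loss is assumed. A stratified sensitivity analysis might be enough.

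Most of this stands as description: the plan contains no error here, and the loss cannot be sized from the documents. It does not defeat the recommendation. The trial already randomises within age groups, the stratum is recorded, and the trade is one-sided: hundredths of a point given up if age is irrelevant, against up to several points recovered if it matters. A sensitivity analysis would not recover that power, because the primary conclusion would still rest on the chi-square.

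A reader might infer that an unstratified test after stratified randomisation inflates type I error. The calculations show the reverse: it is at or below nominal, apart from discreteness.

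A reader might also extend the point to the time-to-event analysis, where "the log-rank test will be used to compare the distributions in the 2 groups". Section 5.10 says "The secondary outcome measures include time to CR of the chalazion as documented by the subject in the patient diary", but that endpoint may be governed by 7.1.5.2, whose text is not shown, and no gain has been shown for it. The point is therefore confined to the primary test.

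**Conclusion.** Upheld as minor. The primary test does not use the stratum, and no visible analysis does. As far as the omitted stratum goes, the test remains valid; if CR differs by age it is conservative and loses some power.

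Under the stated assumptions, the loss is about 0 with no age effect and roughly 0 to 3 points at a 20-point age gap in placebo CR. It is 2.6 points at 60/25 and 7 points at 70/20, which is an extreme case (both with 20% aged under 12).

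Two readings go too far in opposite directions. One is that the trial is underpowered because of this: the documents show neither an age effect, nor the share aged under 12, nor the basis of the sample size. The other is that a 20-point gap is always harmless: the 0.15 point at 50/30 belongs to that pair of rates, and the same gap costs 0.9 point at 45/25 and 2.5 points at 30/10.

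**What to change.** In 7.1.5.1, make the primary test the two-sided CMH test stratified by age group as randomised (under 12, 12 and over). Report the stratum-adjusted risk difference in CR with its 95% CI; the visible text of that section names a test but no effect estimate. Keep Pearson's chi-square as a prespecified sensitivity analysis. Make the change before unmasking, so that there is no dispute over which test is primary.

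The cost is protocol and SAP wording. It needs no extra subjects, visits or data. The sponsor should check whether 7.1.7, not visible here, refers to the chi-square test and needs matching words.

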7.1.5.2 Key Secondary Analyses

7.1.5.3 Other Efficacy Analyses

All quantitative secondary endpoints will be analyzed using the two-sample t-test (parametric) and the Wilcoxon-Mann-Whitney test (nonparametric). Secondary endpoints that are defined as time-to-event variables will be summarized using the Kaplan-Meier method; the log-rank test will be used to compare the distributions in the 2 groups. The primary and secondary endpoints will also be analyzed in the PP population. All secondary analyses will be conducted using two-sided tests at the $\alpha = 0.05$ level of significance.

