3.5.3 Additional Secondary Outcome Measures

- Change in size of the chalazion from baseline to Days 8 ± 1 and 15 ± 1 . Size of the chalazion will be assessed using a caliper provided for the study and measured as height and width in mm. [REDACTED] See Section 5.7 for full-scale information.
- Change in erythema of the study chalazion from baseline to Days 8 ± 1 and 15 ± 1 . Erythema of the chalazion site itself will be assessed using a 5-point scale (i.e., 0 = no erythema to 4 = severe erythema). See Section 5.8 for full-scale information.
- Change in pain associated with the study chalazion in the study eyelid and eye of the study eyelid assessed in VAS from baseline to Days 8 ± 1 and 15 ± 1 . Pain associated with the chalazion in the study eye and eyelid will be assessed at baseline (pre-dose on Day 1), and on Days 8 ± 1 and 15 ± 1 . Pain assessments will be done at the clinical site using a 100 mm VAS. See Section 5.9 for full-scale information.

The assessment of the chalazion should be done by the same investigator as much as possible throughout the study period.

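### Section 7.1.5.3 gives each quantitative secondary endpoint two co-equal tests at 0.05 with no rule for which decides, and uses baseline only by subtraction

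*Combined protocol and SAP*

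**What the plan says.** Section 7.1.5.3 (Other Efficacy Analyses) sets the method in one sentence: "All quantitative secondary endpoints will be analyzed using the two-sample t-test (parametric) and the Wilcoxon-Mann-Whitney test (nonparametric"). It continues, "All secondary analyses will be conducted using two-sided tests at the" 0.05 level. The section gives no order between the tests, no normality criterion and no rule for a split result. It also repeats the secondary endpoints in the per-protocol population, and Section 7.1.1 repeats the efficacy analyses in the mITT population as a sensitivity analysis.

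The endpoints concerned are in Section 3.5.3. The first begins "Change in size of the chalazion from baseline to Days 8" and runs on to Day 15. Erythema (5-point scale) and pain follow at the same visits, also as changes from baseline. Section 5.9 shows that pain is two separate 100 mm VAS questions, one for the eyelid and one for the eye.

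Section 4.4 says "The randomization will be stratified by age group (<12 years, ≥12 years"). Section 7.1.5.3 names neither the stratum nor the baseline value as a covariate.

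The primary endpoint is handled differently. Section 7.1.5.1 names one test, Pearson's chi-square.

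**The concern.** When two tests are planned on the same data and neither is designated, the conclusion can be chosen after both p-values are known. That matters most where the tests tend to part company, on skewed or zero-heavy scales such as a pain VAS. A report could cite whichever p-value is below 0.05 and still be consistent with the plan.

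The second issue is efficiency. A comparison of change scores fixes the coefficient of baseline at 1. When baseline and follow-up are only moderately correlated, that over-corrects, adds noise, and leaves the estimate sensitive to chance baseline imbalance. The trial already holds the baseline values and the age stratum, so it would give up precision it could have at no data cost.

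**Working it through.** **Inputs from the documents.** The tests and the 0.05 level are from Section 7.1.5.3. The synopsis states "Approximately 260 subjects will be randomized", and Section 3.1 gives 130 per arm. The endpoints are from Sections 3.5.3 and 5.9. Section 3.4.2 says size, pain and erythema are not assessed once the chalazion is judged absent, and Section 7.1.8 does not impute missing quantitative data. The analysed number is therefore below 130 per arm by an unstated amount.

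**Inputs assumed.** The documents give no SD, distribution, effect size or baseline correlation for these endpoints. The check uses several shapes, 130, 90 and 60 per arm, and correlations of 0.3 to 0.7.

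**Step 1: count the comparisons.** With size taken as one measure, there are 4 measures (size, erythema, eyelid pain, eye pain) × 2 visits = 8 comparisons. Two tests each give 16 p-values in the ITT population. Repetition in mITT and PP gives 16 × 3 = 48.

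**Step 2: check the nominal level.** The 0.05 is a setting, not a derived figure. Under no effect (20,000 simulated trials per scenario), each test alone rejected in 4.5% to 5.3% of trials, so each holds its level.

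**Step 3: error if either test may count.** Two independent tests would give 1 − 0.95² = 9.75%. These two are highly correlated, so the figure is lower. Simulated chance under no effect that at least one p-value is below 0.05:

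| Assumed shape | 130 per arm | 90 per arm | 60 per arm |
|---|---|---|---|
| Normal | 0.0590 | 0.0595 | 0.0625 |
| 5-point erythema change | 0.0590 | 0.0583 | 0.0580 |
| t, 3 df | 0.0687 | 0.0670 | 0.0653 |
| Exponential | 0.0702 | 0.0714 | 0.0722 |
| Zero-heavy pain change | 0.0727 | 0.0775 | 0.0719 |
| Lognormal | 0.0760 | 0.0784 | 0.0741 |

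The range is 5.8% to 7.8%, an excess of 0.8 to 2.8 points. The simulation standard error is about √(0.07 × 0.93 / 20,000) = 0.002.

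**Step 4: error if both tests were required.** P(both) = P(t) + P(Wilcoxon) − P(either). For lognormal data at 130 per arm, 0.0451 + 0.0491 − 0.0760 = 0.0182. For the erythema shape, 0.0529 + 0.0498 − 0.0590 = 0.0437. Under that reading the error stays below 5%.

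**Step 5: disagreement when there is an effect.** For a lognormal outcome (log-scale SD 0.8, log-scale shift 0.22), one test is significant and the other is not in 22.0%, 19.6% and 16.3% of trials at 130, 90 and 60 per arm. For a change between two correlated lognormal values (correlation 0.3 to 0.6, 130 per arm), which is closer to the planned endpoint, the figure is 17% to 20%.

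**Step 6: what baseline adjustment gains.** With equal variance σ² at baseline and follow-up and correlation ρ:

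- Change score: variance 2σ²(1 − ρ).
- ANCOVA: variance σ²(1 − ρ²).
- Ratio: (1 − ρ²) / [2(1 − ρ)] = (1 + ρ)/2.

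At ρ = 0.3 this is 1.3/2 = 0.65, at 0.5 it is 1.5/2 = 0.75, and at 0.7 it is 1.7/2 = 0.85. Sample size cancels, so the ratios hold for whatever number is analysed. If the two variances differ (σ_X at baseline, σ_Y at follow-up), the change-score variance exceeds the ANCOVA variance by (σ_X − ρσ_Y)². That is never negative, but its size would differ from the ratios above. No gain was calculated for the age stratum.

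**The case against.** **The plan does not say that either test suffices.** This stands. A reader might infer that the plan's real significance level is above 5%. The documents do not support that: they are silent on how the pair is read, and requiring both would give less than 5%. The defect is the missing rule. The 6% to 8% figure describes one reading that the text leaves open.

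**Baseline is used.** This also stands. A reader might infer from the unadjusted tests that baseline is ignored, but Section 3.5.3 defines the endpoints as changes from baseline. What is lost by not also using it as a covariate is precision, not validity.

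**The number of endpoints matters more than the second test.** Correct. With normal data at 130 per arm, the chance of at least one false positive across the 8 comparisons is 25% to 34% with the t-test alone and 29% to 39% with either test (correlation between endpoints 0.5 down to 0). A hierarchy might sit in the key secondary sections (3.5.2, 5.12, 7.1.5.2), which are redacted or show no text, so its absence cannot be asserted. Section 7.1.5.3 itself has visible text, and that text does not rank the two tests.

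**A linear model is not ideal for every endpoint.** Correct for erythema, a 5-point ordinal score. In the skewed scenario of Step 5 the rank test was also more powerful than the t-test. This shapes the fix but does not justify leaving both tests co-equal.

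**Responders drop out of these comparisons.** Correct. A reader might want to turn the variance ratios into power at 130 per arm. The documents do not support that, because resolved chalazia are neither measured nor imputed. ANCOVA would also be more precise on a subset selected after randomization, which does not remove any selection bias.

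**Conclusion.** The point holds in a limited form. For 8 endpoint-by-visit comparisons the visible plan leaves open which of two tests decides. If either may be claimed, the error per comparison is about 6% to 8%. On a skewed scale with a moderate effect, about one trial in five would give a split result with no rule to settle it. Separately, leaving baseline out as a covariate forgoes a reduction in variance to about 65% to 85% of the change-score value.

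The error and disagreement figures rest on assumed distributions, and the variance ratios on assumed correlations of 0.3 to 0.7 with equal variances at the two times. None of these can be checked against the documents. No absolute power figure should be attached.

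The reach is confined to quantitative secondary endpoints. A reader might extend the worry to the main efficacy claim, but the primary analysis is a single chi-square test on complete response and is unaffected.

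**What to change.** In Section 7.1.5.3, replace the paired-test sentence with one decisive analysis per endpoint:

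- **Size and the two pain VAS scores:** ANCOVA of the change (or visit value) with treatment, baseline value and age stratum as terms. Report the Wilcoxon-Mann-Whitney test as supportive.
- **Erythema:** one pre-stated baseline-adjusted ordinal or rank-based analysis, for example a proportional-odds model with treatment, baseline score and age stratum. Any other test is supportive.
- **Split results:** state that the conclusion follows the decisive analysis.

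The cost is a wording change and a standard model, with no new data. The small downside is reliance on a model for skewed data, which is why the rank test stays as a sensitivity check.

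The missing size, pain and erythema values after resolution (Sections 3.4.2, 5.7, 5.9 and 7.1.8) need their own solution. This change does not address them.
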